2. HYPOTHESIS

We hypothesize that the use of serratus plane blocks for ambulatory breast surgery postoperative analgesia will provide improved pain relief while resulting in decreased opioid usage and opioid-related adverse events such as nausea and vomiting, thus improving patient recovery and satisfaction.

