3. SPECIFIC AIMS

The primary objective of this study is to determine if the use of serratus plane blocks placed before outpatient breast surgery, provide superior pain control to standard of care, as evidenced by decreased opioid consumption.

Secondary objectives include assessments of pain, anti-emetic use, incidence and severity of opioid related-adverse events including postoperative nausea and vomiting and overall patient experience and satisfaction.

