- the study design (e.g., the number of participants);
- the details of each pain management regimen (including their risks and benefits);
- how patients are assigned to the investigational and control groups (i.e., randomly);
- the methods by which the study will monitor the patient's pain;
- risks/benefits;
- participation in this study is not required for receipt of either postoperative analgesia; regimen;
- patients may withdraw from this study at their discretion;
-

9. **EXPERIMENTAL DESIGN**

a. Overview:

This is a randomized, double-blind, placebo-controlled trial of serratus plane block in subjects undergoing unilateral or bilateral breast surgery at Long Island Jewish Medical Center. Ninety subjects will be enrolled into the study at presurgical testing approximately one week before their surgery. Subjects will be stratified based on surgery type and randomized to receive a serratus plane block with either bupivacaine HCL or normal saline in a 1:1 ratio. All patients will receive standard intraoperative anesthesia and standard postoperative pain control.

- **Control Group:** Each patient in the control group will receive standard intra-operative general anesthesia and standard post-operative pain control as well as a placebo injection of normal saline on the operated side(s) using the same technique as the serratus plane block.
- **Investigational Group:** Each patient in the investigational group will receive serratus plane blocks on the operated side(s) using bupivacaine HCl. This will be in addition to standard of care intra-operative anesthesia and standard of care post-operative pain control. One (unilateral) or two (bilateral) 20mL bolus of drug, 0.25% of bupivacaine.HCl, will be administered underneath the fascia of the serratus muscle for each subject using ultrasound guidance. The total amount of bupivacaine administered will be 50mg or 100mg for unilateral and bilateral procedures, respectively.

b. Randomization:

The Biostatistics Unit (BU) will develop a computer-generated randomization list that utilizes a permuted block design, and will develop and implement a well-documented double-blind randomization procedure. Details of the procedure, including required record keeping, will be further developed upon approval of this protocol.

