Postoperatively, pain intensities at rest and on movement will be assessed every 30 minutes in the PACU for the first four hours and at hourly intervals up until PACU discharge, using the visual analog scale (VAS) with two anchor points; 0 being no pain and 10 being the worst pain imaginable. Following discharge patients will be asked to record their pain upon and one hour after taking their pain medication up until the end of the first postoperative day.

3. ***Postoperative Nausea (Incidence and rating).***

Evaluation will be performed at every 30 minutes in the PACU for the first four hours and at hourly intervals up until PACU discharge using a standard 11-point verbal rating scale, for which “0” represents “no nausea” and 10 represents “worst nausea imaginable.” Significant nausea is defined as a score of ≥ 4 .

4. ***Vomiting.***

This will be recorded throughout PACU stay until discharge. Vomiting will be measured as the number of emetic and retching (recorded separately) episodes occurring at least 1 minute apart during entire PACU stay. Severe vomiting will be defined as 3 or more episodes during a given time interval. Vomiting and retching episodes will be counted as necessary up to PACU discharge.

5. ***Amount of antiemetic administered.***

Amount of antiemetic administered intra-operatively, during PACU and hospital stay will be recorded.

6. ***PACU Length of Stay.***

7. ***Patient Experience and Satisfaction.***

Patient satisfaction with postoperative pain and and overall patient satisfaction with their surgical experience will be assessed within one week following discharge with a follow up phone call using a 5-point categorical scale.

i. Statistical Considerations

1. **Brief Summary:** This is a double blind randomized, placebo controlled trial of Bupivacaine vs Placebo for the treatment of post-op pain following outpatient breast surgery.
2. **Primary Endpoint:** Narcotics usage (IV or PO) for first 4 hours in the PACU, expressed as morphine equivalents (ME) .
3. **Secondary Endpoints:** Narcotic usage for the duration of PACU and hospital stay and up to postoperative day one, antiemetic administration in PACU (no, yes); PACU length of stay, Self-reported pain using the 0–10 Numeric Pain Rating Scale during the first 4 hours of PACU stay, hospital stay and up until the end of the first postoperative day. Self-reported nausea, vomiting episodes during PACU stay and patient satisfaction with pain management.

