4. **Statistical Methods:**

Primary - Analysis of covariance (ANCOVA) with “type of surgery” as a covariate will be used to compare mean ME between the two groups. (The inclusion of these covariates in the model is in accordance with ICH E9 Section 5.7 guidelines.) Data transformation (presumably a log transform) will be considered in order to achieve the required assumptions of normality and equal variance.

Secondary – The chi-square test will be used to compare anti-emetic rates and patient satisfaction. ANCOVA will be used to compare LOS, pain and nausea scores.

5. **Intention to Treat (ITT):** The ITT population will be defined as all subjects who are randomized. All primary analyses will be carried out on the ITT population.
6. **Sample Size Considerations:** A two-sample t-test approach is used as a reasonable simplification of the ANCOVA method. Based on previous data, it is expected that the Placebo group will average 12 ME (SD=4) of narcotics in the PACU. A reduction of 20% to 9.6 ME in the Bipuvacaine group would be clinically significant. A sample size of n=45 subjects per group (total 90) will yield 80% power to detect such a reduction (alpha=0.05, 2-tailed t-test).
7. **Interim Analysis:** There will be no interim analysis for early stopping of the trial.

j. Adverse events

An adverse event (AE) is any untoward medical occurrence in a clinical investigation of a patient administered a pharmaceutical product and that does not necessarily have a causal relationship with the treatment. An AE therefore is any unfavorable and unintended sign (including an abnormal laboratory finding), symptom or disease temporally associated with the administration of an investigational product, whether or not related to the investigational product. An unexpected AE is one of a type not identified in nature,

severity, or frequency in the study protocol or of greater severity or frequency than expected based on the information in the study protocol.

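### Optional improvement to a secondary endpoint: a five-point satisfaction rating is compared by chi-square, where a stratified ordinal test would have more power if the block shifts ratings roughly evenly across the scale

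*Combined protocol and SAP*

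**What the plan says.** All references are to the combined protocol and SAP.

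- **Test (9.i.4, secondary methods):** "The chi-square test will be used to compare anti-emetic rates and patient satisfaction". One sentence covers both outcomes. It gives no cut-point, trend test or stratification for satisfaction.
- **Scale (9.h.7):** satisfaction is obtained within a week of discharge "with a follow up phone call using a 5-point categorical scale". Category labels are not given.
- **Direction (Section 2):** the block is expected to reduce pain, opioid use and opioid-related events, "thus improving patient recovery and satisfaction".
- **Which rating:** 9.h.7 collects two ("Patient satisfaction with postoperative pain and and overall patient satisfaction with their surgical experience will be assessed"). Section 3 names "overall patient experience and satisfaction" as an objective. The endpoint list in 9.i.3 has only "patient satisfaction with pain management", and 9.i.4 does not say which rating it means.
- **Strata (9.a and 9.b):** "Subjects will be stratified based on surgery type", with three types. Surgery type is also the covariate in the primary ANCOVA.

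**The concern.** The other outcome in the chi-square sentence is binary: "antiemetic administration in PACU (no, yes" in 9.i.3. For that outcome the test is the usual choice. A five-point rating is different. A Pearson chi-square on the 2 x 5 table gives the same result however the columns are arranged, and it spreads four degrees of freedom over every possible difference, although the hypothesis concerns one kind of difference, a move towards higher satisfaction. If the scale is instead to be collapsed to two groups, part of the rating is lost and the cut remains to be chosen.

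At stake is the chance of seeing a benefit that the protocol names in its hypothesis and objectives. The ratings and the randomisation factor are already collected. The primary endpoint is not involved, and the trial claims no power for satisfaction.

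**Working it through.** **1. The plan's own figure.** Section 9.i.6 gives means of 12 and 9.6 ME, SD 4, 45 per group, two-sided alpha 0.05. The standardised difference is (12 - 9.6)/4 = 0.6. The noncentrality is 0.6 x sqrt(45/2) = 2.846 on 88 degrees of freedom, and the noncentral t gives 80.4% power. The stated 80% reproduces, and nothing below touches it.

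**2. Inputs for satisfaction.** From the documents: 45 per arm, 1:1 allocation, three strata, five categories. Assumed, because the documents give no figures: the rating distributions, the odds ratios (OR), 15 patients per stratum per arm, and two-sided alpha 0.05 for this endpoint. Control distributions, lowest to highest category:

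- B1: .05, .10, .20, .35, .30
- B2: .20 in each
- B3 (high): .02, .05, .13, .30, .50

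**3. Model of improvement.** Under proportional odds, each cumulative odds C/(1 - C) is divided by the OR. For B1 the cumulative probabilities are .05, .15, .35, .70 and the odds .053, .176, .538, 2.333. Dividing by 2.5 gives .021, .071, .215, .933, hence category probabilities of about .021, .045, .111, .306, .517. The Mann-Whitney probability (ties counted half) is then .05(.990) + .10(.957) + .20(.878) + .35(.670) + .30(.259) = .633.

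**4. Tests.** Pearson chi-square without continuity correction, on five categories or after collapsing. Van Elteren: with mid-ranks r in stratum s, arm sizes n and m, N = n + m, and R the rank sum of one arm, the statistic is the sum over strata of [R - n(N + 1)/2]/(N + 1). It is divided by the square root of the sum of nm x sum{(r - (N + 1)/2)^2}/[N(N - 1)(N + 1)^2].

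**5. Simulated power, five-category chi-square against van Elteren** (at least 20,000 trials per scenario):

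| OR | B1 | B2 | B3 |
|---|---|---|---|
| 1.5 | 10% / 18% | 11% / 19% | 9% / 17% |
| 2 | 24% / 43% | 27% / 45% | 21% / 39% |
| 2.5 | 41% / 65% | 45% / 67% | 35% / 57% |
| 3 | 57% / 79% | 61% / 82% | 49% / 71% |

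The gain is about 8 points at OR 1.5. At OR 2 to 3 it is 17 to 24 points, including runs with strata of 27/12/6 per arm. With no effect, van Elteren rejects in about 5% of trials, so the gain is not inflated type I error. With 38 responders per arm (B1, OR 2.5) the figures are 34% against 57%.

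**6. Against a collapsed scale, OR 2.5:**

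| Control | Top category vs rest | Top two vs rest | Van Elteren | Gain (points) |
|---|---|---|---|---|
| B1 | 56% | 47% | 65% | 9 or 18 |
| B2 | 50% | 56% | 67% | 17 or 11 |
| B3 | 55% | 33% | 57% | 2 or 25 |

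**7. What stratifying adds.** An unstratified Wilcoxon test has almost the same power (65% on B1 at OR 2.5), so nearly all the gain comes from using the order. Stratifying costs up to about 1 point if strata are alike. It adds about 3 to 4 points if they differ by 0.7 on the log-odds scale.

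**8. Where the ordinal test loses:**

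- Improvement only from category 4 to 5, B1 to (.05, .10, .20, .15, .50): chi-square 47%, van Elteren 20%. The Mann-Whitney probability is .05(.975) + .10(.90) + .20(.75) + .35(.575) + .30(.25) = .565, so there is little net rank shift to detect.
- The same move on B3, to (.02, .05, .13, .10, .70): 49% against 32%.
- Polarised responses, B1 to (.20, .05, .10, .15, .50): 83% against 11%.

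**The case against.** **The advantage needs more than a shift in one direction.** A reader might infer that an ordinal test is better, at no cost, for any improvement. That is not so. In the first two cases of step 8 nobody does worse, yet chi-square has more power. A move at the top of the scale is plausible for satisfaction, and the documents give no distribution that would rule it out. This stands and limits the claim to shifts near proportional odds.

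**The effect sizes are assumed.** No odds ratio for satisfaction appears in the documents. At 1.5 the gain is small and neither test is useful. This also stands.

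**The five-category table may not be what is meant.** Pairing satisfaction with antiemetic rates could imply a proportion. Sparse cells also push towards collapsing: on B1 at OR 2.5 the expected count per arm in the lowest category is 45 x (.05 + .021)/2 = 1.6, and in the next 45 x (.10 + .045)/2 = 3.3. This is fair, and step 6 shows that the gain can then be as small as 2 points. But it leaves an unstated cut-point that itself moves power considerably.

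**The endpoint is already named.** The formal list in 9.i.3 does name satisfaction with pain management. What remains is a consistency point: Section 3 names overall experience, and 9.i.4 does not say which rating is tested. It adds nothing to the power argument.

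**Wider readings.** A reader might infer that the planned test is invalid or that the trial's power is in doubt. Neither follows: the test is valid and step 1 reproduces the stated power. Nor does the argument from order carry over to antiemetic use, which is binary.

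**Conclusion.** The point holds as an optional, low-severity improvement to one secondary endpoint. With 45 per arm and a shift near proportional odds, a van Elteren test gains about 8 points over the five-category chi-square at an odds ratio of 1.5 and 17 to 24 points at 2 to 3. Against a collapsed scale at 2.5 the gain is about 2 to 25 points. Under proportional odds from 1.5 to 3 the ordinal test was ahead of both the five-category and the collapsed versions. It falls behind the five-category test when improvement is confined to the top two categories or when responses polarise.

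The sizes rest entirely on assumed distributions, odds ratios and stratum sizes. The facts that need no assumption are that the scale has five ordered points, that the hypothesis is improvement, and that 9.i.4 states neither the coding nor which of the two ratings is tested.

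**What to change.** Before unblinding, replace the satisfaction part of the chi-square sentence in 9.i.4 with:

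> Satisfaction with pain management (5-point scale, not collapsed) will be compared by a van Elteren test stratified by surgery type, reported with category counts by arm and the Mann-Whitney probability (ties counted half) with 95% CI. Overall satisfaction with the surgical experience, if kept as an endpoint, will be analysed the same way.

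State in 9.i.3 whether the overall rating is kept. The category counts let a reader see a change confined to the top of the scale, which the rank test may miss.

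The administrative cost is wording only: the ratings and surgery type are already collected, and no patient, visit or data item is added. The statistical cost is up to about 1 point of power for stratifying if strata are alike, and the loss shown in step 8 if the effect is far from proportional odds.

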A unique randomization number will be generated by the Biostatistics Unit for each subject in the trial with the format RZxyyy. The randomization number will be a 4-digit number with the following format: the 1st digit (x) will designate the **TYPE OF SURGERY** [1=Breast reduction/mastopexy, 2=Breast augmentation, 3= Revisions & Other] and the last 3 digits (yyy) will be numbered sequentially starting with “001”. For example, the third subject randomized to “Breast augmentation” will have the randomization number RZ2003.

Subjects will be randomized to either Placebo (saline) or Bupivacaine injection as described below. Randomization will be double blind. Preparation of blinded injection is described below.

c. Blinding and Injection Preparation:

Sterile, sealed, plastic syringes of clinically available supply of normal saline (0.9%) and bupivacaine.HCl (0.25%) will be prepared aseptically by the unblinded study pharmacist ([name]) at Long Island Jewish Medical Center Pharmacy upon receipt of study physician's orders. The study pharmacist will have access to the full randomization scheme and will prepare the sterile syringe with a 2-part tear off label. Both parts of the label will contain a randomly generated 4-digit number generated by the Biostatistics Unit. In addition to noting the number, one

of these labels will be attached to the drug accountability paperwork when the drug is dispensed. The second part of the label will remain affixed to the syringe and will be attached to data collection sheet by the study anesthesiologist administering the drug. Syringes will be prepared upon receipt of study physicians orders. Any test articles to be administered will be checked by the pharmacist and a second member of LIJ pharmacy.

d. Surgery:

All breast surgery will be performed under general anesthesia as per standard of care. The type of surgery and laterality will be recorded.

1. Opioids will be utilized at the discretion of the study anesthesiologist for intraoperative pain control.
2. Regardless of whether a subject is enrolled in the investigational arm or control arm of the study, the breast surgery will take place in the usual fashion.

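### Antiemetic use is compared by an unstratified chi-square although randomisation is stratified by surgery type: a valid test, but one that loses power if antiemetic use differs markedly between surgery types

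*Combined protocol and SAP*

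**What the plan says.** Section 9.a (Overview): "Subjects will be stratified based on surgery type and randomized", with allocation to "bupivacaine HCL or normal saline in a 1:1 ratio". Section 9.b (Randomization) specifies a "computer-generated randomization list that utilizes a permuted block design" and gives the strata as "1=Breast reduction/mastopexy, 2=Breast augmentation, 3= Revisions & Other". Block size is not stated.

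Section 9.i.4 (Statistical Methods) uses type of surgery as a covariate in the primary ANCOVA and cites ICH E9 for doing so. Among the secondary endpoints, ANCOVA is named for length of stay, pain scores and nausea scores. For antiemetic use, which 9.i.3 lists as a no/yes variable in the PACU, the method is: "The chi-square test will be used to compare anti-emetic rates and patient satisfaction". No stratified test, logistic model or other adjustment is named for it.

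Section 9.h.3 is titled to cover both incidence and rating of postoperative nausea, and sets a threshold: "Significant nausea is defined as a score of" 4 or more. Section 3 also lists the incidence of postoperative nausea and vomiting among the secondary objectives. Section 9.i.4 mentions nausea only as scores.

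**The concern.** The plan treats surgery type as important in its design and in its primary analysis, then drops it for the binary antiemetic endpoint. Balancing the arms within strata removes the between-stratum differences from the true sampling variance of the rate difference. The pooled chi-square still counts those differences as noise. If antiemetic use varies by surgery type, the test's real type I error falls below 5% and its power falls too.

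The hypothesis in section 2 links lower opioid use to less nausea and vomiting, and antiemetic use is one of the measures that bear on it. The trial is sized for morphine equivalents only, so avoidable loss on this endpoint is worth removing if it is cheap to do so.

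The nausea threshold raises a separate question: a definition is written down for an incidence endpoint that no planned analysis uses.

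**Working it through.** **The plan's own figure.** Section 9.i.6 gives 12 against 9.6 ME, SD 4, two-sided alpha 0.05, 45 per group, 80% power. The standardised difference is 2.4/4 = 0.6. A two-sample t-test then needs 44.6 per group, rounded up to 45, and 45 per group gives 80.4% power. The figure reproduces. It concerns the primary endpoint; the plan states no rate or power for antiemetic use.

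**Inputs for the check.** From the documents: 45 per arm, 1:1 allocation, three strata, two-sided 5%. Assumed, because the documents are silent: antiemetic rates by stratum, a common odds ratio of 0.3, equal strata (15 per arm each), and exact balance within strata.

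**Why the chi-square is conservative.** Let stratum k hold a share w_k of each arm and have antiemetic rate p_k under the null, with overall rate p̄ and n per arm.

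- True variance of the rate difference: (2/n) × Σ w_k p_k(1 − p_k)
- Variance the pooled chi-square uses: (2/n) × p̄(1 − p̄)
- Ratio of the two: Σ w_k p_k(1 − p_k) / [p̄(1 − p̄)], which never exceeds 1

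Examples with equal strata:

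- 35/45/55%: [(0.2275 + 0.2475 + 0.2475)/3] / 0.2475 = 0.2408/0.2475 = 0.97
- 25/45/65%: [(0.1875 + 0.2475 + 0.2275)/3] / 0.2475 = 0.2208/0.2475 = 0.89
- 15/50/85%: [(0.1275 + 0.25 + 0.1275)/3] / 0.25 = 0.1683/0.25 = 0.67

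At a ratio of 0.89 the normal approximation gives a true size of about 2 × Φ(−1.96/√0.89) = 3.8%. Simulation gives 3.4%; the gap reflects the discreteness of counts.

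**Simulation.** 200,000 trials per scenario, Pearson chi-square against Cochran-Mantel-Haenszel (CMH), both without continuity correction. Power is at odds ratio 0.3.

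| Assumed control rates | Spread (points) | Type I error, chi-square / CMH | Power, chi-square / CMH | Power given up (points) |
|---|---|---|---|---|
| 45/45/45% | 0 | 4.9% / 4.7% (run at 40% in all strata) | 75% / 74% | −1 (CMH loses) |
| 35/45/55% | 20 | 4.3% / 4.7% | 73.6% / 73.5% | about 0 |
| 30/45/60% | 30 | 3.9% / 4.9% | 71.5% / 72.3% | about 1 |
| 25/45/65% | 40 | 3.4% / 5.0% | 69% / 71% | 2 |
| 20/50/75% | 55 | 2.4% / 4.9% | 62% / 69% | 7 |
| 15/50/85% | 70 | 1.4% / 4.9% | 46% / 63% | 16 before rounding |

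**Robustness.** With unequal strata (22/15/8 per arm) the losses at spreads of 40, 55 and 70 points are about 2, 6 and 12 to 13 points. With blocks of 4, random stratum sizes and incomplete final blocks, the 20/50/75% case barely moves: type I error 2.4% against 4.8%, power 62% against 69%.

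**Continuity correction.** The gain depends on leaving it out. With the 0.5 correction, CMH power is about 66% with no surgery effect (uncorrected chi-square 75%), 62% at 25/45/65% (69%) and 59.5% at 20/50/75% (62%). A corrected CMH would do worse than the uncorrected chi-square in all of these cases. Section 9.i.4 does not say whether its chi-square is corrected.

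**Nausea incidence.** No arithmetic applies. Section 9.h.3 names incidence and defines a threshold, section 3 lists incidence as an objective, and 9.i.4 gives a method only for scores.

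**The case against.** The strongest reply is that nothing is invalid. The chi-square never exceeded 5% in any scenario, the endpoint is secondary, the plan promises no power for it, and the primary analysis already adjusts for surgery type. All of that stands.

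The second reply is that the loss is conditional. The documents show that surgery type was thought relevant to opioid use; they do not say that it predicts antiemetic use. For spreads up to 30 points the two tests are practically equal, and with no surgery effect CMH is about 1 point worse. This stands too, and it limits the point to a modest one.

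Third, antiemetic use is not the only measure of the nausea hypothesis. Section 9.h also has repeated nausea scores, vomiting and retching counts, and the amount of antiemetic given. That is fair.

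Fourth, exact within-stratum balance was assumed although the block size is not given. Incomplete blocks would shrink the effect somewhat, but with blocks of 4 the change was negligible.

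What survives is an imbalance of costs: stratifying loses about 1 point if surgery type is irrelevant, and protects against larger losses if it is not.

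**Conclusion.** The point holds as a minor improvement to a secondary analysis. The planned chi-square is valid but ignores the stratification factor, and it loses power if antiemetic use differs by surgery type: about 0 to 1 point at spreads of 20 to 30 points, 2 at 40, and 7 to 16 at 55 to 70. These figures rest on assumed stratum rates, an odds ratio of 0.3, equal strata and uncorrected tests.

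A reader might infer that the test is conservative in this trial as a matter of fact, or that a substantial share of power is being lost. The documents do not support that: they give no antiemetic rates, overall or by surgery type, and nothing in them points to spreads of 55 points or more. Nor is there any risk of excess false positives from this choice.

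The missing analysis of nausea incidence is a separate omission. It is plain from the text, needs no assumed rates, and has no magnitude attached. It should not be read as adding weight to the power argument.

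**What to change.** In section 9.i.4, replace the chi-square for PACU antiemetic use (no/yes) with a Cochran-Mantel-Haenszel test without continuity correction, stratified by the surgery type used at randomisation, and report a common odds ratio or risk difference with its 95% CI. Logistic regression with treatment and surgery type as factors is an acceptable alternative in keeping with the primary model; the figures above were computed for CMH only. State the absence of the correction explicitly, because software defaults differ and the correction would remove the benefit.

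Separately, add the incidence of significant nausea (score of 4 or more, section 9.h.3) to 9.i.4, analysed by the same method. Since nausea is scored repeatedly in the PACU, say how a subject is classified, for example by any PACU score at or above the threshold.

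The cost is a sentence or two in the analysis section, with no new data and no additional subjects, and about 1 point of power for antiemetic use if surgery type turns out to be unrelated to it.
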